8.4.2 Primary Analysis (or Analysis of Primary Endpoints)

The primary objective of the study is to identify if one or any of the pharmacodynamics biomarkers of interest have predictive utility on the clinical tumor response to neoadjuvant ruxolitinib treatment in patients with operable HNSCC. The clinical response will be based on the reduction in Δtumor size from baseline to 14-21 days of ruxolitinib treatment:

- (1) Primary analysis using Spearman correlation between baseline pSTAT3 expression and %Change in tumor size will also be performed. As a supportive exploratory analysis, for clinical responders of patients who have achieved a 35% or greater on reduction in Δtumor size from baseline, descriptive statistics with mean, standard deviation and 95% CI will be calculated for baseline STAT activation (pSTAT3 expression) and Wilcoxon rank tests will be used to determine the significant difference on baseline pSTAT3 expression between responders and non-responders.
- (2) Primary analysis using Spearman correlation between change of pSTAT3 expression and %Change in tumor size will also be performed. As a supportive exploratory analysis, for clinical responders of patients who have achieved a 35% or greater on reduction in Δtumor size from baseline, descriptive statistics with mean, standard deviation and 95% CI will be calculated for change in STAT activation (pSTAT3 expression) from baseline and Wilcoxon rank tests will be used to determine the significant difference on change of pSTAT3 expression between responders and non-responders.
- (3) Primary analysis using Spearman correlation between change of cyclin D1 expression and %Change in tumor size will also be performed. As a supportive exploratory analysis, for clinical responders of patients who have achieved a 35% or greater on reduction in Δtumor size from baseline, descriptive statistics with mean, standard deviation and 95% CI will be calculated for change in cyclin D1 expression from baseline and Wilcoxon rank tests will be used to determine the significant difference on change of cyclin D1 expression between responders and non-responders.
- (4) Primary analysis using Spearman correlation between baseline genetic or epigenetic PTPRT/PTPRD silencing and %Change in tumor size will also be performed. As a supportive exploratory analysis, for clinical responders of patients who have achieved a 35% or greater on reduction in Δtumor size from baseline, descriptive statistics with mean, standard deviation and 95% CI will be calculated for baseline genetic or epigenetic PTPRT/PTPRD silencing and Wilcoxon rank tests will be used to determine the significant difference on baseline genetic or epigenetic PTPRT/PTPRD silencing between responders and non-responders.
- (5) Primary analysis using Spearman correlation between baseline C-reactive protein level and %Change in tumor size will also be performed. As a supportive exploratory analysis, for clinical responders of patients who have achieved a 35% or greater on reduction in Δtumor size from baseline, descriptive statistics with mean, standard deviation and 95% CI will be calculated for baseline C-reactive protein level and Wilcoxon rank tests will be used to determine the significant difference on baseline C-reactive protein level between responders and non-responders.

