1.4.2 Additional Analysis

To determine if expression of serum proteins or DNA polymorphisms predict response to ruxolitinib targeting, paired serum (baseline, post-treatment) and baseline peripheral blood mononuclear cells (PBMCs) will be isolated. Blood will be processed for serum and isolation of PBMCs. Serum will be analyzed for proteomic markers using mass spectroscopy and luminex ELISA assays. DNA will be isolated from PBMC samples for SNP analysis. Tissue will be processed for DNA, fluorescence in situ hybridization (FISH), tissue microarrays, and

Phase 2 - Ruxolitinib Page 22 of 67

immunohistochemistry microarrays. Both uniplex and multiplex serum cytokine profile analysis, for correlation with other biomarkers and clinical responsiveness will be performed. For specific cytokines of interest, including IL-6, ELISA kits will be used. For multiplex analysis, the technology developed by Luminex Corporation (Austin, TX, http://www.luminexcorp.com) will be used. It enables a laboratory to simultaneously measure up to 100 analytes in a single microplate well, using very small sample volumes (less than 50 microliters). Previous studies have shown that a multi-marker panel offering the highest diagnostic power was comprised of 22 biomarkers, including EGF, EGFR, Cyfra 21-1, AFP, IL-8, MMP-3, CA 72-4, CA 15-3, MMP-2, TNF-RI, IL-7, HCGb, MIF, Mesothelin, MCP-1, IL-1Ra, FGFb, CEA, sVCAM-1, tPAI 1, RANTES, IGFBP-1. Statistical analysis using our novel ADE algorithm resulted in a sensitivity of 84.5%, specificity of 98%, and 92% of patients with active head and neck cancer correctly classified from a cross-validation serum set³⁶. Further proteomic analysis will be performed using IHC microarrays.

2 Objectives of the Study

2.1 **Primary Objective**

To identify baseline and/or pharmacodynamic biomarkers of response to ruxolitinib based upon association with quantitative change in tumor size (ΔTumor size) following 14-21 days of neoadjuvant ruxolitinib in patients with operable HNSCC. We hypothesize that ΔTumor size will correlate with five prioritized, predictive biomarkers which will be designated for specialized alpha spending: 1) baseline expression of pSTAT3; 2) change in expression of pSTAT3; 3) change in expression of the STAT3 target gene cyclin D1; 4) baseline silencing of protein tyrosine phosphatase receptors D or T (PTPRD or PTPRT) by mutation or methylation; 5) baseline elevation in peripheral inflammatory markers (C-reactive protein [CRP]).

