8.2 Determination of Sample Size and Accrual Rate

8.2.1 Sample Size and Power Estimate

The primary objective of the study is to identify baseline and/or pharmacodynamic biomarkers that might have predictive utility to determine the clinical response to ruxolitinib. As a biomarker study, the statistical design is to accrue a sufficient number of patients and provide 80% power to test one or any of 5 key hypotheses with a shared alpha of 0.15: 1) relationship between clinical response (ΔTumor size) and baseline STAT activation (pSTAT3 expression); 2) relationship between clinical response (ΔTumor size) and change in expression of pSTAT3; 3) relationship between responders (ΔTumor size) and change in expression of cyclin D1: 4) relationship between clinical response (ΔTumor size) and baseline genetic or epigenetic PTPRT or PTPRD silencing; 5) relationship between responders (ΔTumor size) and baseline C-reactive protein. An overall alpha of .15 will be shared equally among the five primary hypotheses. 23 patients with complete biomarker data are needed to achieve 80% power for the 5 primary hypothesis and limit overall family wise error rate (FWER) to 15%. As estimated from our prior window trials, accounting for treatment compliance and quality paired tumor specimens, this will require enrollment of 45 patients. For each biomarker (baseline pSTAT3 expression, change from baseline of pSTAT3 expression, change from baseline of cycline D1 expression, baseline PTPRT or PTPRD silencing and baseline C-reactive protein), mean and standard deviation will be estimated and compared for significance between clinical responders and non-responders of ruxolitinib therapy using Wilcoxon rank tests. Our experience with our phase 0 clinical trial testing the STAT3 decoy also showed correlations between ΔKi-67 (the primary pharmacodynamic efficacy endpoint) and STAT3-target genes falling in the range of .50 to .67. Twenty-five patients will enable a two -tailed Spearman Correlation test at alpha = .03 to detect a true correlation of .56. For the expected 30% of patients with a PTPR mutation, a one-tailed Wilcoxon test will demonstrate increased sensitivity to ruxolitinib via a decrease in tumor size equal to 1.3 standard deviations with 23 patients (8 with a mutation).

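### The exploratory responder analysis in 8.4.2 item (4) summarises a present/absent marker (PTPRT/PTPRD silencing) with a mean, SD and 95% CI, which gives unusable intervals when responders are few

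*Combined protocol and SAP*

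**What the plan says.** Section 2.1 lists the marker among the five prioritised ones as "baseline silencing of protein tyrosine phosphatase receptors D or T (PTPRD or PTPRT) by mutation or methylation". No numeric silencing score is defined anywhere. Section 1.3 counts tumors as mutated or methylated, and 8.2.1 counts patients with a mutation (8 of 23).

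Section 8.4.2 item (4) names a Spearman correlation between silencing and percent change in tumor size as the primary analysis. It then adds, introduced by "As a supportive exploratory analysis", a responder comparison based on a reduction of at least 35%. In responders, "descriptive statistics with mean, standard deviation and 95% CI will be calculated for baseline genetic or epigenetic PTPRT/PTPRD silencing". For the comparison, "Wilcoxon rank tests will be used to determine the significant difference on baseline genetic or epigenetic PTPRT/PTPRD silencing between responders and non-responders". The same template is used for pSTAT3, cyclin D1 and CRP in the other items, and a sentence in 8.2.1 likewise lists all five markers for mean, SD and a Wilcoxon test.

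Counts and percentages for categorical variables are promised only in 8.4.3 and 8.4.4. Nowhere does the plan say how the interval is formed, whether the Wilcoxon p-value is exact or approximate, or how many responders are expected.

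**The concern.** A mean and SD suit a measured expression level. For a yes/no marker the mean is a proportion, and a symmetric interval around it misbehaves in a group of a few patients. It shrinks to a point when all or none are silenced, and otherwise tends to run below 0% or above 100%. The zero-width case misleads most, because it shows complete certainty on a handful of patients.

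A rank test on 0/1 data is a test of a 2×2 table. With very small cells a normal approximation to it may be poor.

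At stake is the reported precision, and possibly the reported significance, of the responder-by-silencing table. Section 1.3 presents this marker as a possible basis for selecting patients, so the table is likely to be read closely even though it is exploratory.

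**Working it through.** **Inputs.** From 8.2.1: N = 23 evaluable; 8 with a mutation; overall alpha .15 over five hypotheses, so .15/5 = .03 each. From 1.3: mutation about 30%, PTPRT methylation about 60%. Assumed, because the plan is silent: 0/1 coding, a t-interval, and small responder counts m.

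**The plan's own figure.** The 80% power in 8.2.1 for the mutation hypothesis (one-tailed Wilcoxon, 8 against 15, shift 1.3 SD, alpha .03) reproduces: simulated power .800 in 20,000 runs. There the marker defines the groups and tumor change is ranked, so that calculation does not bear on the exploratory table.

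**Intervals.** With x of m responders silenced, p = x/m, SD = √[p(1−p)m/(m−1)], and the interval is p ± t(.975, m−1) × SD/√m. For 3 of 4: SD = √(.75 × .25 × 4/3) = .5; half-width 3.182 × .5/2 = .796; interval −.046 to 1.546.

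| Silenced / responders | t-interval | Exact (Clopper-Pearson) |
|---|---|---|
| 4/4 | 100% to 100% | 40% to 100% |
| 3/4 | −5% to 155% | 19% to 99% |
| 1/3 | −110% to 177% | 1% to 91% |
| 2/5 | −28% to 108% | 5% to 85% |
| 3/6 | −7% to 107% | 12% to 88% |

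Listing every x for m = 2 to 7, each interval is zero-width or leaves 0–100%. At m = 8 only 4/8 stays inside. At m = 1 the SD has a zero divisor.

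The zero-width case is not rare. With 3 responders and silencing unrelated to response, its chance is .3³ + .7³ = .37 at 30% prevalence and .6³ + .4³ = .28 at 60%.

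**P-values.** Take 3 responders, all silenced, with 8 of 23 silenced overall.
- Silenced patients share midrank 19.5, the others 8. The responder rank sum is W = 3 × 19.5 = 58.5.
- Mean = 3 × 24/2 = 36.
- Tie-corrected variance = (3 × 20/23) × [8 × 15/(23 × 22)] × 11.5² = 81.82; SD 9.045.
- z = 22.5/9.045 = 2.487, two-sided p = .013. With continuity correction z = 22/9.045 = 2.432, p = .015.
- Fisher's exact test: C(8,3)/C(23,3) = 56/1771 = .032. An exact permutation Wilcoxon on these data also gives .032.

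Here the approximation falls below .03 and the exact test does not. Other tables, as approximation without / with correction against Fisher:
- 2/2 responders, 8 silenced overall: .047 / .055 against .111
- 2/2 responders, 7 silenced overall: .029 / .034 against .083
- 5/5 responders, 14 silenced overall: .047 / .053 against .116

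**How often.** Over 24 splits (1 to 6 responders; 7, 8, 14 or 17 of 23 silenced), the true rejection rate of the approximate test at nominal .05 ran from 0 to .116. It exceeded .05 in 6 splits without the correction and in 5 with it.

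**The case against.** The strongest reply is on the p-value. The plan says only that Wilcoxon rank tests will be used. Computed exactly on 0/1 data, that test matches Fisher's: both give .116 for 5 of 5 responders against 9 of 18 non-responders. Even the approximation keeps its level in most splits. A reader might infer that the planned test gives p-values that are too small whenever responders are few. The documents do not support that; they only leave the computation unspecified.

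A reader might also infer, because the text sits under the primary-analysis heading and concerns a prioritised marker, that a primary result is compromised. It is not. Item (4) labels the comparison supportive and exploratory, and the primary test is the Spearman correlation. The plan sets no significance level for the exploratory comparison, so .03 and .05 serve above only as reference points.

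The interval method, the 0/1 coding and the responder count are all inferred. A 95% CI for a 0/1 mean could be computed as an exact binomial interval, and 8.4.3 and 8.4.4 show that the authors' habit for categorical data is counts and percentages. That suggests carried-over wording. It does not rescue item (4) as written: those sections do not govern 8.4.2 and name no interval method, and an SD alongside a mean points to the usual t-interval.

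**Conclusion.** The point holds in a limited form. Item (4) prescribes continuous-variable summaries for a marker that the documents treat as present/absent. On the t-interval reading, no outcome with 2 to 7 responders yields a usable interval. The p-value concern is conditional: the approximation can be roughly two to three times too small in particular tables, while an exact Wilcoxon is sound.

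This rests on three assumptions: yes/no coding, mean ± t × SD/√n, and single-digit responder counts. The plan gives no expected response rate. The example with 8 silenced borrows the plan's mutation count; counting methylation as well would raise it. The importance is minor: the primary Spearman analysis, its .03 alpha share and the sample size are untouched.

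**What to change.** In 8.4.2 item (4), and in the matching sentence of 8.2.1:
- Define silencing as 0/1, stating which mutation and methylation findings count. If a quantitative methylation score is intended, say so instead.
- Replace mean, SD and 95% CI with n/N and percent silenced, with an exact (Clopper-Pearson) 95% CI, in responders and in non-responders.
- Compare the groups with Fisher's exact test, or state that the Wilcoxon p-value is exact.
- Leave the primary Spearman analysis as it is.

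The cost is SAP wording only: no new data, and no change to sample size or alpha.

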8.4.3 Secondary Analysis (or Analysis of Secondary Endpoints)

For secondary endpoints, due to the limited sample size in the study, descriptive statistics with mean and 95% confidence intervals will be used. For continuous variables, descriptive statistics will include the number of non-missing values, mean, standard deviation, median, min and

Phase 2 - Ruxolitinib Page 51 of 67

maximum. For categorical variables, descriptive statistics will include counts and percentages per category. For comparison between subgroups, ANOVA and t-tests or non-parametric tests will be used when appropriate to determine the association of the efficacy endpoints and specific biomarkers. For example, descriptive statistics with mean, standard deviation and 95% CI will be calculated for the tumoral Ki-67 proliferation index and Wilcoxon rank tests will be used to determine the significant difference on the tumoral Ki-67 proliferation index between responders and non-responders. We will also performed additional analysis using Spearman correlation between the tumoral Ki-67 proliferation index and %Change in tumor size.

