2.2 Secondary Objectives

- To assess preliminary efficacy of neoadjuvant ruxolitinib in patients with operable HNSCC as determined by quantitative ΔTumor size
- To describe the tolerability of brief neoadjuvant exposure to ruxolitinib
- To assess the effect of ruxolitinib on the tumoral Ki-67 proliferation index
- To evaluate additional candidate biomarkers of ruxolitinib response or resistance in HNSCC patients as determined by quantitative ΔTumor size, including:
 - Baseline activation and/or modulation of additional JAK/STAT3 signaling pathway proteins
 - o Baseline SHP-2 overexpression
 - Reverse-phase protein array (RPPA) will be conducted on paired pre- and posttreatment tissue as a source of unbiased biomarker discovery

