2.3.2 Secondary Endpoints

- The size of the tumor will be determined and net ΔTumor measurements used to determine the response.
- The safety of this window intervention will be reported descriptively, including tabulation
 of toxicities according to NCI CTCAE v.4, surgical complications, and length of hospital
 stay.
- The Ki-67 proliferative index will be measured in baseline and post-treatment tumor tissue as described, and will serve as a secondary endpoint (pharmacodynamic efficacy).²¹ The five prioritized biomarkers will be analyzed for correlations with ΔTumor size, as above. In addition, they will be analyzed for correlations with ΔKi-67.
- Non-prioritized biomarkers will also be evaluated for correlations with ΔTumor size and ΔKi-67. In order to assess biomarker response to ruxolitinib, we will test each component of the biomarker panel for within-patient differences between the pretreatment and post-treatment biospecimens (tumor tissue and blood) and compute the pvalues for each paired test (either a paired t test or the signed rank test). We anticipate a panel of 15 20 proteins will be tested for short-term modulation with TMAs. P values from paired data will be adjusted to control the expected false discovery rate by the method of Benjamini and Hochberg. Additional analyses of secondary endpoints will be conducted on an exploratory and hypothesis-generating bases using available material. These endpoints may include qualitative and semi-quantitative scoring of IHC in tissue arrays, gene microarrays and serum protein measures.

3 Study Design

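### Section 8.4.3 should analyse the Ki-67 objective as within-patient change; neither test it names for Ki-67 estimates the pre/post effect

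*Combined protocol and SAP*

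**What the plan says.** The secondary objective in section 2.2 reads: "To assess the effect of ruxolitinib on the tumoral Ki-67 proliferation index". The endpoint in section 2.3.2 is built for it: "The Ki-67 proliferative index will be measured in baseline and post-treatment tumor tissue as described". That bullet labels Ki-67 a measure of pharmacodynamic efficacy and adds correlations of the five prioritized biomarkers with ΔKi-67.

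The statistical section that should turn this into an analysis is 8.4.3. It opens by saying that secondary endpoints will be reported descriptively, with means and 95% confidence intervals, because the sample is small. Comparisons between subgroups are then introduced "to determine the association of the efficacy endpoints and specific biomarkers", with Ki-67 as the worked example. For Ki-67 it gives three things:

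- "descriptive statistics with mean, standard deviation and 95% CI will be calculated for the tumoral Ki-67 proliferation index";
- "Wilcoxon rank tests will be used to determine the significant difference on the tumoral Ki-67 proliferation index between responders and non-responders";
- "additional analysis using Spearman correlation between the tumoral Ki-67 proliferation index and %Change in tumor size".

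A paired analysis does appear, in the last bullet of section 2.3.2, on non-prioritized biomarkers. The plan there is to "test each component of the biomarker panel for within-patient differences between the pretreatment and post-treatment biospecimens" by paired t or signed-rank test, for an expected 15-20 proteins, with Benjamini-Hochberg adjustment. Ki-67 is not named as a component.

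**The concern.** In a single-arm window study, the quantity closest to a drug effect on Ki-67 is each patient's change from baseline to the post-treatment specimen. Section 8.4.3 never names that change. A statistician who follows it literally would report whether Ki-67 differs by tumor response and whether it tracks tumor shrinkage. Those are association questions. The question in section 2.2, whether Ki-67 moved on ruxolitinib, would have no specified estimate or test in the statistical section.

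Three choices are left to be made after the data are seen: which value is summarised (baseline, post-treatment or change), which test is used, and whether the result shares a false-discovery adjustment with discovery proteins. Section 1.3 justifies Ki-67 as an endpoint by citing earlier window trials in which it fell on treatment, so the open choices affect an endpoint on which the rationale relies.

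**Working it through.** **1. Does *index* in 8.4.3 mean change?** The neighbouring sections name change when they intend it. Section 8.4.2 items (2) and (3) specify change of pSTAT3 and change of cyclin D1. Section 8.4.4 specifies both baseline and change for STAT1/STAT3 activation. Section 2.3.2 writes ΔKi-67. Section 8.4.3 uses none of these terms for Ki-67, so the reading as change cannot be taken for granted.

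**2. Could the two named tests answer the objective even if *index* meant change?** Let c_i be patient i's post-minus-baseline change, and suppose the drug adds the same shift −δ to every patient, giving c_i − δ.

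- The ranks of c_i − δ are the same as the ranks of c_i for any δ.
- The rank-sum statistic (responders against non-responders) and the Spearman coefficient depend on Ki-67 only through those ranks.
- Both statistics are therefore identical for δ = 0 and for any other δ. The same holds if *index* means the post-treatment value.

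These tests respond only to differences in Ki-67 across tumor response, not to its mean change.

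**3. Simulation check.** Assumptions: 23 patients (the biomarker-evaluable number in 8.2.1), normal changes with mean −d in SD units, Ki-67 change unrelated to tumor change, two-sided .05, and 3,000 runs per row. Responders are the k patients with the most favorable tumor change. The documents give no expected k, so 2, 5 and 8 were tried. Entries are the percentage of runs rejecting.

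| k | d | Rank-sum by response | Spearman | Paired signed-rank |
|---|---|---|---|---|
| 2 | 0 | 4.4 | 4.5 | 5.0 |
| 2 | 0.6 | 4.9 | 5.4 | 75.7 |
| 2 | 1.0 | 4.3 | 5.4 | 99.5 |
| 5 | 0 | 4.3 | 5.2 | 5.2 |
| 5 | 0.6 | 4.7 | 4.6 | 77.2 |
| 5 | 1.0 | 4.7 | 5.5 | 99.6 |
| 8 | 0 | 4.1 | 4.7 | 4.7 |
| 8 | 0.6 | 4.6 | 4.9 | 76.2 |
| 8 | 1.0 | 5.1 | 4.6 | 99.2 |

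The first two tests stay near 5% whatever the true mean fall. The paired test responds to it.

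**4. What a paired analysis would deliver.** The plan states no precision or power for this objective, so there is no figure of its own to reproduce. The SD of the change is not given either, so results are in units of that SD.

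- 95% CI half-width = t(.975, n−1)/√n. With n = 23: 2.074/4.796 = 0.43 SD.
- Smallest mean change detectable with 80% power, paired t-test, two-sided .05, n = 23: 0.61 SD.
- Signed-rank power at 0.6 SD, from the table: about 76-77%.

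The count of 23 Ki-67 pairs is an assumption. Section 8.2.2 ties replacement to having paired data on at least one of the five prioritized biomarkers, and Ki-67 is not one of them. With 20 pairs the half-width is 2.093/4.472 = 0.47 SD; with 25 it is 2.064/5 = 0.41 SD.

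**The case against.** The strongest reply is that the plan already contains what is needed. Section 8.4.3 makes descriptive estimation the rule for secondary endpoints and gives Ki-67 a mean and 95% CI. If that interval is taken on the change, it answers the objective. The responder test is introduced as an example of an association analysis and does not claim to measure the drug effect. The paired tests in 2.3.2 concern proteins on tissue microarrays, and section 1.4.1 lists Ki-67 labeling among the microarray stains, so Ki-67 may well be in the panel.

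Much of this stands, and it rules out several stronger readings that a reader might infer:

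- *That the protocol has no paired analysis, or that 8.4.3 offers Ki-67 nothing beyond two association tests.* Section 2.3.2 plans paired tests that may cover Ki-67, and 8.4.3 includes a descriptive mean with an interval.
- *That the responder test is bound to fail because too few patients reach a 35% reduction.* The documents give no expected responder count, so no minimum p-value can be derived from them.
- *That correlations of the five biomarkers with ΔKi-67 are missing.* Section 2.3.2 already plans them.
- *That adjusting Ki-67 within the Benjamini-Hochberg family would be an error.* It is a legitimate choice; it only needs to be stated.

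What the reply does not remove is the gap. The interval in 8.4.3 has no time point and no change. In the bullet that holds the paired tests, ΔKi-67 appears as an outcome against which other biomarkers are correlated, not as a panel member. Both rescues depend on inference, and 8.4.3 is where the matter should be settled.

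**Conclusion.** The point holds as a mismatch between an objective and its analysis section. The two tests that 8.4.3 names for Ki-67 carry no information on its mean pre/post change. The descriptive interval could carry it, but is not defined as a change. Whether the paired tests of 2.3.2 include Ki-67 is unstated. The mismatch itself follows from the text and needs no numerical assumption.

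The size figures are illustrative. They assume 23 evaluable Ki-67 pairs and roughly normal changes; on that basis, the half-width of about 0.43 SD and the detectable change of about 0.6 SD (roughly 76-80% power, two-sided .05) show that a paired analysis is feasible at the planned size. No stated design figure is wrong.

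Even when corrected, the estimate is an uncontrolled pre/post change. With no control arm it cannot separate ruxolitinib from sampling differences between the baseline and surgical specimens or from other changes over the window.

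**What to change.** In 8.4.3:

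1. Define the Ki-67 analysis as the within-patient change, post-treatment minus baseline, reported with a 95% CI and a paired test (signed-rank or paired t, as in 2.3.2; choose one in advance).
2. State whether this test belongs to the Benjamini-Hochberg family of the 2.3.2 panel or stands apart from it.
3. Use ΔKi-67, consistent with 2.3.2, in the Spearman correlation with percent tumor change.
4. Keep the responder against non-responder comparison, labelled exploratory, and say which Ki-67 value it compares.
5. State the number of paired Ki-67 specimens and describe the result as an uncontrolled pre/post change.

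The cost is a few sentences. Tumor samples at screening and at surgery are already in the study calendar (Table 6.1), so no new procedure, specimen or patient is needed.
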